Study Protocol

Official Title: The Impact of Different Skin Suture Methods in Episiotomy Repair on Healing and Pain: A Randomized Clinical Trial

NCT06379048

This randomized clinical trial is planned to be conducted at Başakşehir Çam and Sakura City Hospital, a tertiary care center in İstanbul, Türkiye, between March and August 2022, to compare three skin closure techniques—mattress (M-Suture), simple interrupted (I-Suture), and subcutaneous continuous (SC-Suture)—used in episiotomy repair among primiparous women aged 18–45 who underwent vaginal delivery with episiotomy. Patients are planned to be randomly assigned to groups using a computer-generated stratified block design (blocks of 3, 6, and 8), with allocation revealed just before the procedure. Exclusion criteria include multiple births, deep vaginal lacerations, fetal anomalies, operative delivery, coagulopathy, and lateral lacerations. A standardized mediolateral episiotomy and repair technique is planned to be used across groups, and visual models is planned to be employed to ethically standardize the novel suturing approaches. Pain and healing are planned to be assessed using the REEDA and Visual Analog Scale (VAS) scores on postpartum days 1 and 15. Statistical analyses are planned to be conducted using SPSS v23, with ANOVA for group comparisons and significance set at $p < .05$. The study is planned with a sample size of 132 to ensure 80% power at a 5% significance level, accounting for a 10% attrition rate.

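### Allocation is called stratified, but no factor is named and the planned ANOVA mentions no stratum term; if prognostic strata were used, some power is forgone

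*Combined protocol and SAP*

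**What the plan says.** The whole plan is one unnumbered paragraph under the title Study Protocol, so no other section can supply missing detail.

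- **Randomisation sentence:** "computer-generated stratified block design (blocks of 3, 6, and 8), with allocation revealed just before the procedure". Block sizes are given; no stratification factor or level is.
- **Analysis sentence:** "Statistical analyses are planned to be conducted using SPSS v23, with ANOVA for group comparisons". It does not say one-way, and it mentions no stratum term, covariate or model.
- **Outcome sentence:** "Pain and healing are planned to be assessed using the REEDA and Visual Analog Scale (VAS) scores on postpartum days 1 and 15". That makes four comparisons (two scales, two days), all covered by the same analysis sentence.
- **Sample size sentence:** "a sample size of 132 to ensure 80% power at a 5% significance level, accounting for a 10% attrition rate". No effect size, standard deviation or primary outcome accompanies it.
- **Setting and population:** one hospital, with the trial dated "between March and August 2022, to compare three skin closure techniques", and the techniques "used in episiotomy repair among primiparous women aged" 18 to 45.

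**The concern.** The design statement and the analysis statement do not connect. Stratified blocking forces the arms to be similar on the strata. If the strata predict the outcome, the differences between arm means then carry almost no stratum variation, but the residual of an arm-only ANOVA still contains all of it. The F ratio has too large a denominator, so it rejects a true null less often than 5% of the time and is less efficient than a model that includes the strata.

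At stake is efficiency, not validity: power that the design has already paid for may go unused. A second consequence is that a reader cannot tell which model will be fitted, because the plan identifies neither the strata nor the model.

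**Working it through.** **1. The plan's own figure.** The total of 132 cannot be reproduced, because no effect size or standard deviation is given. It is consistent with two readings of the 10% attrition allowance:

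- 120 evaluable × 1.10 = 132
- 118 evaluable / 0.90 = 131.1, rounded up to 132

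Solving the one-way ANOVA power equation backwards for 3 arms, alpha 0.05 and 80% power gives Cohen's f = 0.287 with 120 evaluable and 0.290 with 118. I use f = 0.288 with 119 evaluable (132 × 0.90 = 118.8).

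**2. Inputs not in the plan (assumptions).** The share of outcome variance explained by strata (R²) is taken as 0, 0.05, 0.10 and 0.20. Other assumptions are 2, 3 or 4 equally likely strata with equally spaced effects, equally spaced arm means, allocation as near 1:1:1 as the blocks allow, and blocks of 8 filled 3/3/2.

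**3. Power with strata in the model, analytically.** With normal errors, the noncentrality parameter is λ = N f² / (1 − R²), on 2 and N − 3 − (strata − 1) degrees of freedom.

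- Arm only: λ = 119 × 0.288² = 9.87; critical F(2, 116) = 3.074; power 79.9%.
- With two strata (denominator df 115, critical F 3.075):

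| R² | λ | Power |
|---|---|---|
| 0 | 9.87 | 79.9% |
| 0.01 | 9.97 | 80.3% |
| 0.02 | 10.07 | 80.8% |
| 0.05 | 10.39 | 82.0% |
| 0.10 | 10.97 | 84.2% |
| 0.20 | 12.34 | 88.4% |

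With four strata (df 113) each power is lower by no more than 0.02 point compared with two strata.

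**4. Size and power by simulation.** The arm-only test under stratified allocation does not follow the standard F distribution, so it was simulated: 132 women, blocks of 3, 6 or 8 chosen at random within stratum, 10% random loss, 80,000 trials per setting. The 95% simulation error is about 0.15 point on size and 0.3 point on power. Results for two strata:

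| R² | Size, arm only | Power, arm only | Power, adjusted | Power forgone |
|---|---|---|---|---|
| 0 | 5.2% | 79.7% | 79.7% | 0.0 |
| 0.05 | 4.5% | 80.0% | 81.7% | 1.7 |
| 0.10 | 3.9% | 80.3% | 84.0% | 3.7 |
| 0.20 | 2.8% | 81.0% | 88.1% | 7.1 |

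The size of the adjusted test was 5.0% to 5.2% in all 12 settings. With three or four strata, arm-only size stayed within 0.1 point and each power within 0.2 point of the table, except that adjusted size and power are unaffected in any material way. At R² = 0 with four strata, power was 79.9% arm-only against 79.6% adjusted: the largest cost of adjusting, 0.3 point.

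**5. Independent check.** A separate simulation (120 evaluable, two strata, f = 0.287, normal errors, 10,000 null and 5,000 alternative trials per setting) gave arm-only size of 4.7%, 3.5% and 2.6% at R² 0.05, 0.10 and 0.20. Power, arm-only against adjusted, was 79.9 vs 81.9%, 81.6 vs 85.0% and 81.5 vs 88.1%. Direction and size agree.

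**6. What the strata could be.** One hospital rules out centre, and restriction to primiparous women rules out parity. Age, with an eligible range of 18 to 45, remains possible. The block of 8 cannot be shared equally by three arms (8 / 3 = 2.67), so the randomisation sentence needs clarifying in any case.

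**The case against.** The strongest reply is that no analysis error has been shown. Three things must all be true: strata were used, they predict REEDA or VAS, and the model omits them. The plan establishes none of these. An ANOVA can include a stratum factor, and silence in a one-paragraph summary is weak evidence that it will not. If the allocation was merely blocked, the planned analysis is right as written. Nor does the arm-only test miss the plan's own target of "80% power at a 5% significance level": its simulated power is about 80% to 81% throughout, so the 2 to 7 points are a gain above target. The R² range has no anchor in the plan; at 0.01 or 0.02 the gain is only about 0.4 or 0.8 point, and one R² need not hold for both scales on both days. The block of 8 is a separate problem and says little about whether strata exist.

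Nearly all of this stands, and it is why the point is minor and conditional. It does not remove the point. The plan says it stratifies; analysing by the groups used in allocation is the better method if that is true, and it costs almost nothing if the strata turn out to be uninformative. If it is not true, the word is wrong. Either way the text needs a change.

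**Conclusion.** The concern holds as a minor point about efficiency and specification. It is certain that the plan calls the allocation stratified, names no factor and mentions no stratum term. The rest is conditional on strata having been used and being prognostic. Over assumed R² of 0.05 to 0.20, the arm-only ANOVA has a true size falling from about 4.4% to about 2.8% and forgoes about 2 to 7 points of power on a comparison powered at 80%. Type I error is not inflated and the planned power is not reduced. With R² near zero nothing material is lost. Confidence is medium: the existence, recording and prognostic value of the strata cannot be judged from the plan.

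**What to change.** - **If strata were used:** name them and their levels in the randomisation sentence, and analyse each REEDA and VAS comparison on days 1 and 15 by ANOVA (general linear model) with arm plus the randomisation strata as fixed effects.
- **If allocation was only blocked:** delete the word *stratified* and keep the ANOVA on arm.

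The first option costs 1 degree of freedom with two strata or 3 with four, and at most about 0.3 point of power if the strata explain nothing. SPSS fits the model through its GLM procedure. It does require each woman's stratum in the analysis dataset. The plan does not confirm that, and recruitment is dated 2022, so the change is cheap only if the stratum was recorded at allocation. The second option costs nothing.

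### The planned ANOVA names no covariates and no strata, although both outcomes are first scored after the repair; it is valid, but a prespecified ANCOVA on pre-allocation measures could be more precise at almost no cost

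*Combined protocol and SAP*

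**What the plan says.** The protocol is a single unnumbered paragraph. Four of its statements bear on this point.

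- Outcome timing: "Pain and healing are planned to be assessed using the REEDA and Visual Analog Scale (VAS) scores on postpartum days 1 and 15". Both time points follow skin closure, and no pre-repair score or wound measure is named.
- Analysis: "Statistical analyses are planned to be conducted using SPSS v23, with ANOVA for group comparisons", with a 5% significance threshold. No covariate, regression model or stratum term appears.
- Randomization: a "computer-generated stratified block design (blocks of 3, 6, and 8), with allocation revealed just before the procedure". The stratification factors are not named.
- Size: "The study is planned with a sample size of 132 to ensure 80% power at a 5% significance level", "accounting for a 10% attrition rate". No effect size, SD, primary outcome or primary time point is given.

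The paragraph also limits wound variation by design. It enrols primiparous women only, standardizes the mediolateral episiotomy and its repair, and excludes operative delivery, deep vaginal lacerations and lateral lacerations.

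**The concern.** Women differ before the skin is closed, for example in incision length or in the size of the baby. If such differences predict REEDA or VAS, an ANOVA on suture group alone counts them as noise. The same holds for the stratification factors: they shape the randomization but do not enter the named analysis.

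With roughly 39 or 40 evaluable women per arm, precision is worth having. Because neither score has a pre-repair value, the usual baseline adjustment is not available, and day 1 is the only earlier score in the data. It is not a substitute. It follows the allocated suture, so adjusting for it, or analysing change from it, would remove part of the effect under study. The plan does not propose this, but it does not rule it out either.

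**Working it through.** **Inputs from the protocol:** 132 women, three arms, 80% power, alpha 0.05, 10% attrition. **Assumed:** equal allocation, and R², which is varied.

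**1. The plan's own figure.** The 132 cannot be reproduced, because no effect size or SD is stated. Only the attrition step can be checked: 118/0.9 = 131.1, rounded up to 132; or 120 × 1.10 = 132. The evaluable number behind the plan is therefore about 118 to 120.

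**2. Starting point.** For a one-way ANOVA with three arms, power = P(F′(2, N−3, λ) > F crit), where λ = N·f². Solving for 80% power:

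- N = 118: f = 0.2895, λ = 118 × 0.2895² = 9.89.
- N = 120: f = 0.287.

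If one arm differs from the other two by d SD, then f = d·√2/3, so at N = 118, d = 0.2895 × 3/√2 = 0.614 SD. The 80% is imposed here by solving for f; it does not confirm the plan's power.

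**3. ANCOVA with q covariates.** Residual df = N − 3 − q, and λ = N·f²/(1 − R²). With N = 118 and q = 2 or 3:

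| R² (assumed) | λ | Power | Gain, points | ANOVA N of equal information, 118/(1−R²) | Residual SD ratio, √(1−R²) |
|---|---|---|---|---|---|
| 0 | 9.89 | 79.97% | −0.03 | 118 | 1.000 |
| 0.05 | 10.41 | 82.1% | 2.1 | 124 | 0.975 |
| 0.10 | 10.99 | 84.2% | 4.2 | 131 | 0.949 |
| 0.20 | 12.36 | 88.4% | 8.4 | 148 | 0.894 |

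Starting from 120 evaluable gives the same powers to within 0.1 point, so the reading of the attrition step does not matter. Stratum terms use further degrees of freedom. With eight adjustment terms in all (three covariates plus an assumed five for strata) and R² = 0, power is 79.9%.

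**4. Chance imbalance.** At 39 per arm, the standard error of a between-arm difference in a covariate is √(2/39) = 0.226 SD. The chance of a difference above 0.3 SD is about 19% for one given pair of arms (0.3/0.226 = 1.32 standard errors) and 38% for at least one of the three pairs. With an assumed covariate–outcome correlation of 0.4, a 0.3 SD imbalance moves the outcome contrast by 0.4 × 0.3 = 0.12 SD. The unadjusted contrast has the same standard error of 0.226 SD, so the shift is 0.12/0.226 = 0.53 of one standard error. It lies within the uncertainty that the ANOVA already reports.

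**The case against.** The strongest reply is that nothing is broken. Unadjusted ANOVA after randomization is unbiased and controls type I error, and its standard error already allows for chance imbalance. That stands. A reader might infer that imbalance distorts the suture comparisons; step 4 of the working does not support this. Nor would adjusting for a few measured factors rule out imbalance in unmeasured ones.

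A reader might also infer that ANCOVA would restore power the trial has lost. The documents do not show a shortfall. The 80% has no effect size or SD behind it, and if the number was set on the unadjusted SD, adjustment adds power above the target.

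R² is unknown and may be low. Standardizing the episiotomy, enrolling only primiparous women and excluding the more complicated deliveries all narrow wound variation. Nothing in the protocol shows that incision length, birth weight or age predicts either score. This stands too, and it is why the gain is given as a range starting at zero.

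Stratification limits imbalance on the strata, but they are unnamed, so it cannot be assumed that they cover wound severity. If they are prognostic, leaving them out of the model keeps their variance in the error term. That argues for adjustment.

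Finally, effect size, primary outcome and primary time point are more basic gaps. That is fair, but it does not make this inexpensive change less useful.

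**Conclusion.** The point holds as a question of efficiency, not of validity. Both outcomes are first measured after the allocated suture, and the one named analysis leaves prognostic pre-repair and stratum variation in the error term. From an assumed 80% starting point, adjustment for two or three pre-allocation measures is worth about 0, 2, 4 or 8 points of power at R² of 0, 0.05, 0.10 or 0.20. It costs about 0.03 point if the measures are not prognostic. These figures assume equal arms, about 118 to 120 evaluable women and the overall three-group F test.

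The documents support neither a claim of bias nor a claim that power has fallen below the stated level. The change is still worth making, because its possible gain far exceeds its cost.

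**What to change.** Replace the analysis sentence, before any outcome is seen, with a prespecified ANCOVA (general linear model in SPSS):

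- Model each REEDA and VAS score on suture group, the randomization strata (to be named) and two or three named measures fixed before allocation is revealed.
- Suitable examples are episiotomy length and birth weight. If no new measurement is wanted, use maternal age and birth weight; that birth weight can be taken from the delivery record is an assumption.
- Report adjusted between-suture differences with confidence intervals, and keep the unadjusted ANOVA as a sensitivity analysis.
- State that day-1 scores are not used as a covariate and that change from day 1 is not analysed.
- Confirm that allocation is revealed after the episiotomy is made and before the repair. If it is revealed earlier, episiotomy length is not a pre-allocation measure, and the age and birth-weight option should be used.

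The cost is 2–3 of 115 residual degrees of freedom (118 − 3) plus any stratum terms, a brief recording step if episiotomy length is chosen, and a few lines of analysis text. No additional women are needed.
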